2.2.1.2.2 Rat Toxicity Study

Sprague Dawley rats were dosed with L9LS to evaluate toxicity and toxicokinetics. Rats received 0, 40, or 400 mg/kg by IV bolus injection twice (Day 1 and Day 11). Female rats were dosed with 10 mg/kg by SC injection once (D1); male rats were dosed with 10 mg/kg SC twice (D1 and D11); both male and female rats were dosed with 100 mg/kg SC twice (Day 1 and Day

11). For all dose levels, the main group was necropsied at Day 12 to evaluate potential immediate effects, and recovery animals were necropsied at Day 46, to evaluate the potential for delayed effects and recovery. Treated rats exhibited a transient increase in body temperature post-dose (up to + 0.5°C, considered a non-adverse response). Serum clinical chemistry tests detected slightly increased globulin, consistent with the administration of L9LS, an IgG MAb. For IV dosing, the no observed adverse effect level (NOAEL) was the high dose, 400 mg/kg IV x2. For SC dosing, the NOAEL was the high-dose, 100 mg/kg SC x2. SC injection of L9LS did not cause reactogenicity (edema, erythema, eschar) in any rat. Histopathology evaluation of the skin at the SC injection site reported minimal to moderate SC mixed cell infiltration, considered treatment related and predictive for human volunteers. One treated rat (in the 100 mg/kg SC group) was found dead; this event was attributed to a procedural error the previous day and is not considered treatment related. One treated female (in the 100 mg/kg SC recovery group) had grossly visible heart enlargement (2-fold increase in both heart weight and heart-body weight compared to the control means), with normal heart histology. Spontaneous cardiomyopathies are occasionally observed for the Sprague Dawley strain of rat. Based on the singular incidence, this observation is not considered treatment related.

With reference to the US Food and Drug Administration (FDA) Center for Drug Evaluation and Research 2005 Guidance for Industry Estimating the Maximum Safe Starting Dose in Initial Clinical Trials for Therapeutics in Adult Healthy Volunteers, scaling based on body weight is appropriate for a MAb expected to distribute mainly in the vascular space. The rat IV NOAEL of 400 mg/kg x2 supports the IV clinical high dose with a 20-fold dose margin. The rat SC NOAEL of 100 mg/kg x2 supports the SC clinical dose with a 20-fold dose margin.

The FDA provides guidance on "the nonclinical safety studies recommended to support human clinical trials" in the Guidances for Industry ICH M3(R2) Nonclinical Safety Studies for the Conduct of Human Clinical Trials and Marketing Authorization for Pharmaceuticals and ICH S6 Addendum to Preclinical Safety Evaluation of Biotechnology-Derived Pharmaceuticals. Taken together, the L9LS TCR and rat toxicity study results meet the safety standard set in these guidances and support proceeding with L9LS clinical trials.

2.2.1.3 Clinical Experience

L9LS was evaluated in a phase 1, dose-escalation, open-label clinical trial with experimental CHMI to evaluate safety and protective efficacy of L9LS in healthy, malaria-naive adults at the VRC. The phase 1 trial at the VRC was a two-part, dose-escalation, adaptive-design study evaluating the safety, tolerability, PK, and protective efficacy of L9LS.

Doses evaluated ranged from 1 to 20 mg/kg delivered via IV administration, and 5 mg/kg delivered via SC administration. No safety concerns were identified. A total of 17 L9LS recipients and 6 control participants underwent CHMI. Of the 17 participants who received a

single dose of L9LS, 15 (88%) were protected after CHMI. Parasitemia did not develop in any of the participants who received 5 or 20 mg/kg of IV L9LS. Parasitemia developed in 1 of 5 participants who received 1 mg/kg IV, 1 of 5 participants who received 5 mg/kg SC, and all 6 control participants through 21 days after CHMI. Protection conferred by L9LS was seen at serum concentrations as low as 9.2 µg/mL. Thus, in this small phase 1 trial, L9LS administered IV or SC protected recipients against malaria after controlled infection, without evident safety concerns, and all IV and SC administrations were well tolerated. 15

For the first proof-of-concept study with CIS43LS in Malian adults, CIS43LS was administered by the IV route at doses of 40 mg/kg and 10 mg/kg. The first generation anti-malaria MAb CIS43LS was shown to be safe and conferred complete protection against controlled Pf infection in a phase 1 study in healthy adult volunteers at the VRC. CIS43LS was evaluated in a completed phase 2 study of adults in Mali (ClinicalTrials.gov Identifier: NCT04329104). For the first proof-of-concept study with CIS43LS in Malian adults against intense seasonal transmission, CIS43LS was administered by the IV route at doses of 40 mg/kg and 10 mg/kg. No significant safety concerns were noted. By time-to-event analysis, compared to placebo at 6 months, CIS43LS efficacy was 88.2% (adjusted 95% CI, 79.3 to 93.3; P<0.0001) for 40 mg/kg, and 75.0% (adjusted 95% CI, 61.0 to 84.0; P<0.0001) for 10 mg/kg Together, the phase 1 and 2 trials of CIS43LS provide proof of concept that a MAb with an extended half-life can safely confer protection against Pf infection.

As a follow-up to the VRC phase 1 L9LS study, we conducted a phase 2 trial in Mali to assess the safety and efficacy of a single subcutaneous injection of L9LS against P. falciparum infection in healthy children aged 6-10 years over a 6-month malaria season (ClinicalTrials.gov number, NCT05304611). In Part A, safety was assessed at three escalating dose levels in adults, followed by two escalating dose levels in children aged 6-10 years. In Part B, children aged 6-10 years were randomly assigned (in a 1:1:1 ratio) to receive 150 mg of L9LS, 300 mg of L9LS, or placebo. The primary efficacy end point, assessed in a time-to-event analysis, was the first P. falciparum infection detected on blood-smear examination, which was performed at least every 2 weeks for 24 weeks. A secondary efficacy end point, assessed in a time-to-event analysis, was the first episode of clinical malaria. At enrollment, all the participants received artemetherlumefantrine to clear possible P. falciparum infection. In Part B, 225 children underwent randomization; 75 were assigned to each trial group. Subcutaneous injection of L9LS was well tolerated and there were no serious adverse events. At 6 months, the efficacy against P. falciparum infection of 300 mg of L9LS as compared with placebo was 69.9% (adjusted 95%) confidence interval [CI], 50.1 to 81.9; P<0.001), and the efficacy of 150 mg of L9LS as compared with placebo was 66.0% (adjusted 95% CI, 45.0 to 79.0; P<0.001). At 6 months, the efficacy against clinical malaria of 300 mg of L9LS as compared with placebo was 77.4% (adjusted 95% confidence interval [CI], 55.0 to 88.7; P<0.001), and the efficacy of 150 mg of L9LS as compared with placebo was 67.0% (adjusted 95% CI, 39.0 to 82.0; P<0.001). In

summary, subcutaneous administration of L9LS to children was protective against *P. falciparum* infection and clinical malaria over a 6-month malaria season in Mali without evident safety concerns.

Based on the increased potency of L9LS in pre-clinical models, its higher concentration (150 mg/mL), and the lower weight of infants and children, we administered L9LS by the SC route, which is the optimal route for application in this age group. As a follow-up to the phase 1 VRC study, this protocol is designed to evaluate the safety and efficacy of L9LS administered SC in healthy children ages 5 months to 10 years in a setting of perennial high malaria transmission in western Kenya. Kenya is currently participating in the RTS,S/AS01 pilot scheduled to end in May 2023. The immediate catchment area of Siaya County Referral Hospital is a control area, so children are not receiving RTS,S/AS01 or any other malaria chemoprevention currently.

2.2.2 Laboratory Assessments of L9LS

Some laboratory assessments in this study are designed to characterize the investigational product. This includes PK analysis and evaluation for anti-drug antibody (ADA) development after product exposure. Other assays may also be completed from stored samples at a later date. The KEMRI laboratories at Siaya County Referral Hospital and at the Kisian campus in Kisumu will process blood and store coded samples and will either perform sample testing or ship coded samples to designated research laboratories at LIG/NIAID and VRC/NIAID or other approved collaborators for assays that cannot be performed in Kenya. The key to the code will remain at KEMRI. See section 0 for schedules, blood volumes, and tube types to be used for research sample collection. Research assays will be performed on samples from both study product recipients and placebo controls at baseline and throughout the study.

Tube types for clinical labs are according to institutional requirements and are shown in section 0 to estimate blood volumes. Different tubes for clinical evaluations may be used to meet site requirements. In some instances, coded samples may be transported directly by study staff to the laboratory of an approved collaborator.

2.2.2.1 PK Analysis

Concentrations of L9LS will be measured by a Meso Scale Discovery LLC-based automation platform and similar methodology as previously described for other VRC MAb products. 17

2.2.2.2 Detection of Anti-Drug Antibodies

Assays for detection of ADA will be performed at specified timepoints following product administration and compared to baseline status using a similar methodology as previously described for other VRC MAb products. 17

2.2.2.3 Measures of MAb-Mediated Protection Against Pf infection and Clinical Malaria

L9LS-mediated protection against naturally occurring Pf infection will be assessed and compared to control subjects. The endpoint defining MAb-mediated protection from Pf infection is the absence of Pf parasites in blood samples obtained from L9LS-recipients collected from day 7 through week 52 (day 196) after study agent administration (and the same for the part 2 extension). The criterion for a case of Pf infection is based on blood smear analysis.

Giemsa-stained thick blood films will be prepared and examined by trained personnel following the standard operating procedure (SOP) based on the standard WHO protocol. Thick blood smears will be prepared from the blood remaining in the collection device, or (at timepoints when no blood collection is planned) from a finger prick sample. The smears will be examined microscopically.

As secondary endpoints, L9LS-mediated protection against clinical malaria will be assessed and compared to control subjects from day 7 through week 24 (month 6) after study agent administration. The two definitions of clinical malaria in this protocol are 1) an illness accompanied by measured fever $\geq 37.5^{\circ}$ C in the previous 24 hours, and Pf asexual parasitemia > 5,000 parasites/ μ L as detected from microscopic examination of thick blood smear, and 2) an illness accompanied by measured fever $\geq 37.5^{\circ}$ C, or history of fever (subjective or objective) in the previous 24 hours accompanied by any level of Pf asexual parasitemia as detected from microscopic examination of thick blood smear that requires administration of anti-malarial treatment.

Clinical malaria will be assessed by both passive surveillance (unscheduled sick visits) and active surveillance (medical history, physical exam, and blood smear at all scheduled visits), but the blood smear will be read in an expedited manner, ideally within one hour, only if the medical history and/or physical exam are suggestive of clinical malaria. Otherwise, blood smears will be read within 48 hours by two independent microscopists. Children with a positive blood smear, regardless of symptoms, will be treated with artemether-lumefantrine (AL), the first-line antimalarial in Kenya. If the child has already departed the clinic, a treatment course of AL will be sent to the child's home with a community interviewer (ideally within 72 hours of taking the blood smear), who will counsel the parent/guardian about treating the child with the full course. Thick and thin blood smears will be prepared from the blood remaining in the collection device, or from a venipuncture or finger prick sample when clinically indicated (or at timepoints when no other blood collection is planned). Giemsa-stained thick and thin blood films will be prepared and examined microscopically by trained personnel following the SOP based on the standard WHO protocol. Thick and thin blood smears will be used for diagnosis throughout the study.

Additionally, another secondary endpoint, *Plasmodium* 18S ribosomal ribonucleic acid (rRNA) RT-PCR, will be performed by [name], University of Washington. The assay will be applied to dried blood spots using methods substantially equivalent to those reviewed extensively by the FDA for Biomarker Qualification of the 18S rRNA by the University of Washington for CHMI trials (Biomarker Qualification Letter DDTBMQ000044, Oct 12, 2018). The assay has been validated for use on dried blood spots.

Research blood samples may also be used for Pf malaria parasite genome analysis that will be conducted by [name], Harvard School of Public Health.

2.2.3 Repeat Dosing: ADA, PK

All MAbs are potentially immunogenic and can result in the formation of ADA, particularly with repeated dosing. ^{18,17} An ADA response can result in diminished efficacy by altering the PK properties of the MAb, and can also promote adverse reactions to the MAb, including infusion reactions and local and systemic immune reactions. ^{18,19} In the case of the widely used tumor necrosis factor (TNF)-alpha inhibitor MAbs, rates of ADA formation are generally higher in patients treated with chimeric anti-TNF constructs compared with fully human MAbs. ^{20,19} Formation of ADA to anti-TNF MAbs has also been linked to subtherapeutic serum MAb levels that may occur during intermittent dosing. ^{21,20} Moreover, some studies suggest that intramuscular and subcutaneous administration of MAbs is more immunogenic than intravenous administration. ^{21,20}

As described above, L9 is a fully human IgG1 MAb that was modified with the Fc region LS mutation (L9LS) to increase neonatal Fc receptor (FcRn) binding and consequent antibody half-life. Other human IgG1 MAbs with LS mutations produced by the VRC that target HIV and Ebola have been tested in over 30 clinical trials, and ADA has not been observed to date, including in individuals who received up to five administrations of the same MAb. For example, VRC01 was found to be safe and well tolerated at doses ranging from 5-40 mg/kg administered IV and at 5 mg/kg SC in clinical trials that involved HIV-infected and non-infected adults. 17,22-24 In these studies, VRC01 retained its expected neutralizing activity in participants' serum and no ADA responses were detected over the course of multiple administrations. ADA responses against the anti-malarial MAbs CIS43LS and L9LS have not yet been assessed in serum samples collected during the phase 1 US trials 11,15 or the ongoing phase 2 trials in Mali.

Regulatory authorities in the US and Europe request premarketing evaluations for immunogenicity (ADA testing) for all novel biologics. FDA recommends the following regarding the implementation of ADA testing in clinical trials:

"FDA recommends that sponsors obtain **pre-treatment samples** from all subjects. Because there is the potential for pre-existing antibodies or confounding components in the matrix, understanding the degree of reactivity before treatment is essential. The sponsor should obtain

subsequent samples, with the timing depending on the frequency of dosing. Optimally, samples taken 7 to 14 days after the first exposure can help elucidate an early IgM response. Samples taken at 3 to 6 weeks after the first exposure are generally optimal for determining IgG responses. IgA responses may peak earlier than IgG responses, at around 2 to 3 weeks after antigen exposure (Schütz et al. 2013; Macpherson et al. 2008). For individuals receiving a single dose of a therapeutic protein product, these time frames may be adequate. However, for subjects receiving a therapeutic protein product at multiple times during the trial, the sponsor should obtain samples at appropriate intervals throughout the trial and obtain a sample approximately 30 days after the last exposure. For products with long half-lives, samples should be obtained approximately five half-lives after last exposure."

"Samples to determine serum concentrations of the therapeutic protein product should be obtained at the same time as immunogenicity samples. Testing such samples can provide information on whether the therapeutic protein product in the samples is interfering with ADA testing and whether ADA is altering the therapeutic protein product's pharmacokinetics."

In addition to measuring ADA in the pre-MAb administration samples (already collected in the first year of the study), the protocol extension will follow FDA recommendations by collecting serum samples for PK and ADA testing before re-dosing of L9LS/placebo and periodically after re-dosing. The final assessment time point (Day 364) represents approximately 6.5 half-lives after the last exposure since the estimated half-life of L9LS was 56 days in the phase 1 US trial.

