Based on data from Mali suggesting that doses higher than 20mg/kg are needed to protect for 12 months, we propose to assess the safety of an additional two doses: 30 mg/kg and 40 mg/kg in a similar fashion. This extension of part 1 will include an additional 24 children, and will utilize a similar design to before, with 12 participants in each age-dose group in a 3:1 ratio of L9LS to placebo; all participants will be followed for a total of 3 months. However, given that it appears that the younger children are clearing the product more quickly than older people, we will include only children aged 5-71 months, as these are the ages of the children to be included in the part 2 extension. As before, we will ensure safety out to 7 days before proceeding to dose additional subjects.

Part 2: Efficacy study

A total of 324 children 5-59 months of age will be randomized to receive a 10-20 mg/kg dose of L9LS or placebo by SC administration. There will be two L9LS cohorts, one 5-17 months of age and another 18-59 months of age, which will constitute one L9LS arm. A placebo arm will be composed of children 5–59 months of age. They will be followed over 12 months with monthly blood smear microscopy and polymerase chain reaction (PCR) and twicemonthly symptomatology and care-seeking behavior questionnaires. Dosing will be based on three weight bands; all doses will be administered SC with fixed doses of 75 mg L9LS, 150 mg L9LS, or 225 mg L9LS, resulting in a range of 10-20 mg/kg in a double-blinded fashion. Blood will be drawn to assess antibody titers at baseline, and at three additional time points over 12 months to establish pharmacokinetics (PK). Participants in the L9LS arm will be

randomized 1:1 at baseline to receive either a second L9LS injection or a placebo injection to evaluate the additional efficacy of a second dose administered 6 months after the first dose. (Those in the placebo arm will receive a second injection of placebo.) Participants will be followed for an additional 6 months after the second injection with monthly blood smear microscopy and PCR, and a blood draw at month 11 to assess L9LS PK.

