|---|----------|---|---------------|----------------|-------------------|-------------------|------|--------------|--------------|---------------|----------------|----------------|--------------------|---------------------|---------------------|--------|----------------|----------------|----------------|----------------|----------------|----------------|----------------|-----------------------------------|
| Window (d | ays) | Before Parasit Clearance ⁰ | -21 to -14 | - | +1 | ±1 | ±1 | ±7 | ±7 | ±7 | ±7 | ±7 | ±7 | +1 | ±1 | ±1 | ±7 | ±7 | ±7 | ±7 | ±7 | ±7 | ±7 | duled †² |
| Study agent administration | | | | X 5 | | | | | | | | | X 5 | | | | | | | | | | | |
| Adverse events | | | X | X | X | X | X | X | X | X | X | X | X | X | X | X | X | X | X | X | X | X | X | |
| Labora | tory Eva | aluatio | ns | | | | | | | | | | | | | | | | | | | | | |
| Test | Tube | | (Bloo | d volı | ıme i | n mL) |) | | | | | | | | | | | | | | | | | |
| CBC with differential | EDTA | | 0.1 | 0.1 | | | 0.1 | 0.1 | | | | | 0.1 | | | 0.1 | | | | | | 0.1 | | |
| ALT, Cr | SST | | 0.2 | 0.2 | | | 0.2 | 0.2 | | | | | 0.2 | | | 0.2 | | | | | | 0.2 | | |
| Blood smear and dried blood spot for Pf RT-PCR | - | | 0.4 | 0.4 | | | 0.4 | 0.4 | 0.4 | 0.4 | 0.4 | 0.4 | 0.4 | | | 0.4 | 0.4 | 0.4 | 0.4 | 0.4 | 0.4 | 0.4 | 0.4 | 0.4 |
| PK studies | SST | | 3.19 | | | | | 3.1 | | | | | | | | | 3.1 | | | | | 3.1 | | |
| Serum storage | SST | | (X) | | | | | (X) | | | | | | | | | (X) | | | | | (X) | | |
| ADA | SST | | (X) | | | | | (X) | | | | | | | | | (X) | | | | | (X) | | |
| Daily volume | ` / | - | 3.8 | 0.7 | - | - | 0.7 | 3.8 | 0.4 | 0.4 | 0.4 | 0.4 | 0.7 | - | - | 0.7 | 3.5 | 0.4 | 0.4 | 0.4 | 0.4 | 3.8 | 0.4 | |
| Cumulative vo (mL) | olume | - | 3.8 | 4.5 | 4.5 | 4.5 | 5.2 | 9.0 | 9.4 | 9.8 | 10.2 | 10.6 | 11.3 | 11.3 | 11.3 | 12.0 | 15.5 | 15.9 | 16.3 | 16.7 | 17.1 | 20.9 | 21.3 | - |

Abbreviated Title: Anti-malaria MAb in Kenyan children

Version 6.0 Date: 2 Apr 2024

Abbreviations: ADA, anti-drug antibodies; ALT, alanine transaminase; CBC, complete blood count; Cr, creatinine; D, day; EDTA, ethylenediaminetetraacetic acid; HIV, human immunodeficiency virus; M, month; Pf, *Plasmodium falciparum*; PK, pharmacokinetics; SST, serum-separating tube; RT-PCR, reverse transcription polymerase chain reaction.

(X) indicates that no additional blood will be drawn; the test will be performed from the tube shown in the preceding row.

Footnotes:

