- ⁰ The Consent for the extension phase visit can take place during the Day 364 close-out visit for part 2 or thereafter anytime before the extension phase parasite clearance visit. The extension phase pre-enrolment visit must take place within 3 months of the (year 1) Day 364 visit.
- ¹ Home-based visits.
- ² At any time during the study, the subject may have an unscheduled illness visit if experiencing malaria symptoms or other symptoms. The subject may be referred for standard care according to local guidelines.
- ⁴ The first dose of dihydroartemisinin-piperaquine will be directly observed in the clinic if possible, but might be given in the participant's home. The subsequent 2 doses given over the following 2 days will be observed by guides in the subject's home or at the clinic. All dihydroartemisinin-piperaquine doses will be completed prior to day 0 and will be initiated between 21 and 14 days prior to D0.
- ⁵ L9LS or placebo. All other study procedures must be completed prior to study agent administration. Subjects who received L9LS at day 0 will receive L9LS at month 6; those in the placebo arm will receive a second placebo injection at 6 months (if a two-dose regimen is used). Each subject will be monitored for at least 60 minutes after study agent administration and vital signs will be recorded 1 hour after study agent administration. Prior to discharge, subject will be assessed for local reactogenicity (including pain/tenderness, swelling, redness, bruising, and pruritus at the site of injection) and systemic reactogenicity (including fever, feeling unusually tired or unwell, muscle aches, headache, chills, nausea, and joint pain). If the subject is assessed as being unwell or has ongoing reactogenicity symptoms, he or she will be asked to remain in the clinic until evaluation and discharge by a study clinician. Clinicians will follow any solicited symptoms that are ongoing until they have resolved.
- ⁸ Collected prior to study agent administration. Other indicated tests may be performed after study agent administration.
- ⁹ For PK, 3.5 mL serum will be collected prior to malaria treatment administration.
- * The timing of all visits subsequent to Day 168 (administration of dose 2) will be in relation to the Day 168 visit, whenever that occurs; for example, if the Day 168 visit occurs on Day 161, the first day of the window, the Days 169 and 171 home visits will occur 1 and 3 days later (so on days 162 and 164 in relation to dose 1).

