4.1.1 Year 2 Follow-on Study (Safety and Extension)

Part 1b. Follow-on Safety

As part of the follow-on study, an initial dose escalation study will assess the safety and tolerability of 30 mg/kg L9LS and 40 mg/kg L9LS. An additional 12 children ages 5 – 71 months will be randomized to receive L9LS at 30 mg/kg (weight-based dose) or placebo in a 3:1 ratio. If no safety signals are seen after 7 days, an additional 12 children aged 5 – 71 months will be randomized to receive L9LS at 40 mg/kg (weight-based dose) or placebo in a 3:1 ratio. If no safety signals are seen then the follow-on extension will move forward, pending DSMB review of the data and approval to proceed. Children will be followed for a total of three months after dosing. Subjects will be followed at study visits 1, 3, 7, 14, 21, and 28 days after administration, and then at month 2 and month 3.

Follow-on part 2 extension

In the extension phase, all parents/guardians of participants who are currently enrolled in the part 2 efficacy study will be invited to extend their child's participation for approximately 13 months from the time of re-consenting. Parents/guardians of children can be consented to allow participation of their children in the extension phase at any time before their termination in part 2 and up to 3 months after their part 2 close-out. Participants will remain in their same randomization groups from part 2. Those who received two doses of L9LS in part 2 will also receive two doses of L9LS, six months apart, in the extension phase. Those who received one dose of L9LS will receive one dose (plus a dose of placebo six months later), and those who received two doses of placebo will receive an additional two doses of placebo, six months apart.

Before study agent administration, all subjects will be given dihydroartemisinin-piperaquine to clear any preexisting Pf blood-stage infection. Subjects will be followed at study visits 1, 3, 7, and 28 days after administration, and then will have alternating biweekly home visits and clinic visits, identical to the visit schedule during year one, up through 52 weeks after the initial follow-on extension dose in year two. Primary study assessments include medical history, physical examination, and blood collection for pharmacokinetics (PK), anti-drug antibody (ADA) assessments, identification of Pf infection by microscopic examination of thick blood smears and RT-PCR, and other research laboratory evaluations.

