In the ongoing phase 2 trial of L9LS in Mali involving healthy children aged 6-10 years, a prespecified exploratory analysis of the relationship between the weight-based dose of L9LS (mg of L9LS administered per kg of body weight) and protective efficacy suggested that ~12 mg/kg of L9LS corresponds to a protective efficacy against clinical malaria of approximately 75% over six months compared to placebo. In addition, preliminary PK analysis indicates that the average half-life of L9LS in Malian children is ~35 days, compared to ~55 days in Malian adults, and ~65 days in U.S. adults. After receiving 10-20 mg/kg of L9LS, the average number of days required for the serum concentration of L9LS to fall below the lower limit of detection (0.61 μg/mL) was 243 (95% CI 232–254). Therefore, we anticipate that a single dose of L9LS in the range of 10-20 mg/kg will not provide high-level protection (>75%) against malaria over 12 months in healthy Kenyan children 5-59 months of age who are exposed to intense perennial malaria transmission. Therefore, the 1-year extension of the phase 2 Kenya trial will assess the safety and protective efficacy of L9LS at a dose range of 20-40 mg/kg.

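### The 6.5 half-lives in section 2.2.3 run from the first extension dose; in arm 1 the last PK/ADA sample falls 168 days after the last L9LS dose, which is 3.0 half-lives at 56 days or 4.8 at 35 days

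*Combined protocol and SAP*

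**What the plan says.** Section 2.2.3 quotes regulatory guidance on ADA sampling, including "For products with long half-lives, samples should be obtained approximately five half-lives after last exposure", and states that the extension will follow it. In support, it says the final assessment time point, Day 364, "represents approximately 6.5 half-lives after the last exposure since the estimated half-life of L9LS was 56 days". That half-life comes from the phase 1 trial in US adults.

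Four other places bear on the sentence:

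- **Dosing.** Section 4.1.1: "Those who received two doses of L9LS in part 2 will also receive two doses of L9LS, six months apart, in the extension phase". Table 1 gives arm 1 the same regimen. The schedule in 1.4.4 marks study agent at Day 0 and Y2D168.
- **Sampling.** The PK and ADA rows of 1.4.4 are marked at pre-enrolment, Y2D28, Y2D196 and Y2D336. The Y2D364 cells are empty.
- **Visit timing.** Under the asterisked footnote to 1.4.4, visits after the second dose "will be in relation to the Day 168 visit, whenever that occurs".
- **Half-life.** Section 4.2.2 reports that "the average half-life of L9LS in Malian children is ~35 days, compared to ~55 days in Malian adults, and ~65 days in U.S. adults", and the abstract says of Part 1b that "it appears that the younger children are clearing the product more quickly than older people".

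**The concern.** A count of half-lives after last exposure has to start at the last dose of L9LS and end at the last sample tested for ADA. The 6.5 does neither for arm 1: it starts one dose too early and ends at a visit where no PK/ADA tube is drawn.

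Detecting ADA and correlating it with L9LS PK is a primary objective of the extension. The guidance quoted in 2.2.3 gives the reason that timing matters; of paired concentration samples it says: "Testing such samples can provide information on whether the therapeutic protein product in the samples is interfering with ADA testing". The 6.5 is the only half-life count that the section offers for compliance. It is wrong for the arm with the most repeat exposure, where ADA is of most interest. A reader relying on it would think almost no product remains at the last ADA sample, whichever half-life applies.

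**Working it through.** **Inputs**

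- Half-life used in 2.2.3: 56 days.
- Half-lives in 4.2.2: about 35 days (Malian children), 55 (Malian adults), 65 (US adults).
- Arm 1's last L9LS dose: Y2D168 (1.4.4, 4.1.1, Table 1).
- Last PK/ADA sample: Y2D336, window ±7 days, timed from the Y2D168 visit (1.4.4).
- Benchmark: about five half-lives after last exposure (2.2.3).

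**Is the last tube really at Y2D336?** The PK, ADA and volume rows of 1.4.4 each have the same number of cells as the column headings, so the marks map without ambiguity. The daily volumes from Y2D175 to Y2D364 read "0.7 | 3.5 | 0.4 | 0.4 | 0.4 | 0.4 | 3.8 | 0.4". At Y2D336 the 3.8 mL is 0.1 (CBC) + 0.2 (ALT, Cr) + 0.4 (smear and dried blood spot) + 3.1 (PK tube). At Y2D364 the 0.4 mL is the smear and dried blood spot alone. The cumulative row agrees: 17.1, 20.9, 21.3 mL.

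**The plan's figure**

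364 / 56 = 6.5. It reproduces exactly, but only with Day 0 as the last exposure.

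**Arm 1, from the last dose to the last sample**

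336 − 168 = 168 days.

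| Half-life | At 168 days | With window (161–175 days) |
|---|---|---|
| 35 days | 168/35 = 4.8 | 4.6–5.0 |
| 56 days | 168/56 = 3.0 | 2.9–3.1 |
| 65 days | 168/65 = 2.6 | 2.5–2.7 |

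The half-life at which 168 days equals five half-lives is 168/5 = 33.6 days. Five half-lives would take 5 × 35 = 175 days or 5 × 56 = 280 days.

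A tube at Y2D364 would not restore the figure: 364 − 168 = 196 days, and 196/56 = 3.5 (196/35 = 5.6).

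**Approximate fraction of the last dose remaining** (single-phase first-order decline)

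- Implied by 6.5 half-lives: 2^−6.5 = 1.1%.
- At 4.8: 2^−4.8 = 3.6%.
- At 3.0: 2^−3 = 12.5%.

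Section 9.5.6 plans a two-compartment model, so these show order of size only.

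**Arm 2.** The interval depends on what arm 2 receives at month 6, and the documents disagree. Sections 4.1.1 and 6.1.1 and Table 1 describe an arm given L9LS and then placebo. Footnote 5 of 1.4.4, as worded, gives L9LS at month 6 to everyone who had it at Day 0.

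- Last L9LS dose at Day 0: 336/35 = 9.6 and 336/56 = 6.0.
- Last L9LS dose at Y2D168: 4.8 and 3.0, as in arm 1.

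Neither reading gives 6.5 at 56 days, because the last sample is at Y2D336.

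**The case against.** The strongest reply is that little is lost in practice.

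- **The benchmark is approximate, and 35 days is the only half-life given for children.** At 35 days arm 1 reaches 4.8, or 4.6–5.0 across the visit window, and faster clearance in younger children would raise it. This stands: it would be wrong to say that sampling is inadequate. But the 35 days is preliminary and comes from children aged 6–10 years, no half-life is given for the Kenyan children, and 2.2.3 rests its claim on 56 days.
- **Other parts of the guidance are met.** It also asks for samples at intervals throughout and one about 30 days after the last exposure. Y2D196 is 28 days after the Y2D168 dose, so arm 1's ADA plan does not rest on Y2D336 alone. This stands, and the corrected text should say so.
- **Nothing is derived from the sentence, and ADA is already paired with L9LS concentration.** True: no dose, visit or sample size depends on it, and PK and ADA share a tube. The effect of residual product on a negative ADA result depends on the assay's drug tolerance, which the documents do not give, so no such effect is asserted here.
- **The residual percentages are rough, and footnote 5 is a separate matter.** Both points are fair. The arm 1 finding needs neither; footnote 5 matters here only because arm 2's interval cannot be stated until it is settled.

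None of this rescues the 6.5, which is wrong for arm 1 at the section's own half-life.

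**Conclusion.** The concern holds. In arm 1 the last PK/ADA sample is 168 days after the last L9LS dose, not 364. On the 56 days used in 2.2.3 that is 3.0 half-lives, under half the stated 6.5 and short of the five-half-life benchmark. On about 35 days it is 4.8, which approximately meets it. Which applies turns on whether the half-life in these children is near 33.6 days or clearly longer, and the text does not say.

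The interval rests only on the dosing and sampling days in 1.4.4 and on arm 1's regimen in 4.1.1 and Table 1, and is firm to the ±7-day window. The residual fractions assume single-phase decline and are approximate. The defect is a misstated property of the design, offered as support on a primary extension objective. It is not evidence that the ADA results will be invalid.

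**What to change.** - **Section 2.2.3.** Remove the 6.5 and the reference to Day 364. Suggested replacement: *The last extension PK/ADA sample is at Y2D336. In arm 1 this is 168 days after the last L9LS dose: about 4.8 half-lives at the roughly 35 days reported for Malian children, and 3.0 at 56 days (sensitivity). A sample is also taken at Y2D196, 28 days after that dose.*
- **Half-life.** State which value applies to these children and why, given 56 days in 2.2.3 and about 35, 55 and 65 days in 4.2.2.
- **Arm 2.** Reconcile footnote 5 of 1.4.4 with sections 4.1.1 and 6.1.1 and Table 1, then add arm 2's interval.
- **SAP still to be written (section 9.5), optional.** One line: report negative arm 1 ADA results at Y2D336 alongside the paired L9LS concentration.

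The cost is text only: one passage in 2.2.3, one footnote reconciled and, if wanted, one reporting line. Visits, samples and blood volumes stay as they are.
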